#### 2.1.4. Cohort A and Cohort A1 Exploratory Objectives

- To evaluate the efficacy of REGN10933+REGN10987 compared to placebo in preventing SARS-CoV-2 infection assessed by seroconversion in baseline seronegative subjects
- To explore the impact of REGN10987+REGN10933 compared to placebo:
  - On humoral immune response to SARS-CoV-2 infection
  - On measures of infectivity of SARS-CoV-2 as assessed in experimental laboratory assays
- To evaluate the impact of REGN10933+REGN10987 compared to placebo in SARS-CoV-2 infection in subjects who are seropositive at baseline:
  - Prevention of symptomatic infection (strict-term)
  - Prevention of symptomatic infection (broad-term)
  - Prevention of symptomatic infection (CDC definition)
  - Prevention of symptomatic infection (strict-term, CDC definition, or broad-term) or asymptomatic infection
- To explore the relationships between REGN10933+REGN10987 exposure and selected clinical efficacy and safety endpoints and/or biomarkers in seropositive and seronegative subjects
- To assess viral genetic variation in SARS-CoV-2 in subjects with a positive SARS-CoV-2 RT-qPCR
- To explore biomarkers (including host genome variants) associated with safety and efficacy of REGN10933+REGN10987 and to study SARS-CoV-2 (cohort A only)
- To evaluate the impact of treating any household member with anti-SARS-CoV-2 monoclonal antibody on the incidence of SARS-CoV-2 infection among their household contacts. The monoclonal antibody treatment considered for this analysis are any EUA approved antibody any EUA approved antibody including REGN10933+REGN10987 (within or outside of the study R10933-R10987-COV-2067).

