## 8.10. Permitted Medications

Other than the prohibited medications listed in Section 8.9, treatment with concomitant medications is permitted during the study. If there is any question regarding whether a concomitant medication may be used during the study, the study site should contact the medical monitor.

Subjects with symptomatic RT-qPCR confirmed SARS-CoV-2 infection during the study will be treated according to local standard of care as per the discretion of the investigator or treating physician. Any medication used by the study subject should be captured in the concomitant medication eCRF.

Subjects are permitted to receive an approved or EUA approved COVID-19 vaccine after they complete the EAP.

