13. Samples for drug concentration and, immunogenicity, and laboratory testing will be collected based on the subject subset designation as indicated in [Table 4](#)
14. The serology test results will not be communicated to the sites. The sponsor's blinded study team will not have access to post-baseline results associated with subject identification until after the database is locked.
15. During each scheduled or unscheduled visit/contact, the investigator or designee will query subject about AEs in general (see Section [10.1.1](#)) and evaluate if the AEs are associated with SARS-CoV-2 infection, including fever (see Section [9.2.2.2](#)). The investigator should recommend that subjects (themselves or by their parent/guardian) measure their temperature daily during EAP, approximately at the same time, and also every time when the subject feels feverish, chills, or sick. Subjects with symptomatic SARS-CoV-2 infection should be queried on their symptoms weekly until symptoms resolve, even during follow-up period, then follow the regular schedule.
16. The information for the household assessment, including household members who receive an EUA approved monoclonal antibody treatment for COVID-19 or household members participating in the R10933-10987-COV-2067 study, should preferably be collected at the baseline visit. There will be a follow-up assessment at day 29.
17. All subjects will have a weekly NP swab sample collected during the EAP. Only subjects who are RT-qPCR positive will continue to have weekly NP swab samples collected during the follow-up period until 2 consecutive negative ( $\geq 24$  hr) RT-qPCR results or the end of study visit.
18. Only for RT-qPCR positive subjects (cohort A and cohort B): Complete assessments from the time the subject first becomes RT-qPCR positive or from the time they develop symptoms suspected to be COVID-19 (later confirmed by RT-qPCR positive results) until the subject has had 2 negative tests or COVID-19 related symptoms have resolved (whichever lasts longer), or until the end of study visit.

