### 9.2.1. Procedures Performed Only at the Screening/Baseline Visit

The following procedures will be performed for the sole purpose of determining study eligibility or characterizing the baseline population: demographics (eg, age, sex, race, weight, height, etc), medical history, local diagnostic assay for SARS-CoV-2, query for risk factors for SARS-CoV-2 infection (eg, first responder or healthcare worker; presence in outdoor or indoor crowded or public places [without keeping distance >6 feet] in the last 14 days, with or without a mask and/or eye protection; attendance to any social events with more than 10 people in the last 14 days, with or without a mask and/or eye protection; exposure to someone believed to have COVID-19; exposure to someone diagnosed with COVID-19; receipt of influenza vaccine as of July 2020), and household assessment in which subjects will be asked to provide general information about the household members (including their general demographic information, COVID-19 status, their risk of exposure to COVID-19, and treatment with an EUA approved monoclonal antibody treatment for COVID-19).

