1.2.3. Exploratory Objectives

Cohort A and Cohort A1

- To evaluate the efficacy of REGN10933+REGN10987 compared to placebo in preventing SARS-CoV-2 infection assessed by seroconversion in baseline seronegative subjects
- To explore the impact of REGN10987+REGN10933 compared to placebo:
 - On humoral immune response to SARS-CoV-2 infection
 - On measures of infectivity of SARS-CoV-2 as assessed in experimental laboratory assays
- To evaluate the impact of REGN10933+REGN10987 compared to placebo in SARS-CoV-2 infection in subjects who are seropositive at baseline:
 - Prevention of symptomatic infection (strict-term)
 - Prevention of symptomatic infection (broad-term)
 - Prevention of symptomatic infection (CDC definition)
 - Prevention of asymptomatic infection or symptomatic re-infection (strict-term, CDC definition, or broad-term)

- To explore the relationships between REGN10933+REGN10987 exposure and selected clinical efficacy and safety endpoints and/or biomarkers in seropositive and seronegative subjects
- To assess viral genetic variation in SARS-CoV-2 in subjects with a positive SARS-CoV-2 RT-qPCR
- To explore biomarkers (including host genome variants) associated with safety and efficacy of REGN10933+REGN10987 and to study SARS-CoV-2 (cohort A only)
- To evaluate the impact of treating any household member with anti-SARS CoV-2 monoclonal antibody on the incidence of SARS-CoV-2 infection among their household contacts. The monoclonal antibody treatment considered for this analysis are any EUA approved antibody including REGN10933+REGN10987 (within or outside of the study R10933-R10987-COV-2067)

Cohort B and Cohort B1

- To evaluate the impact of REGN10933+REGN10987 compared to placebo in seropositive subjects in preventing:
 - Symptomatic SARS-CoV-2 infection (strict-term)
 - Symptomatic SARS-CoV-2 infection (broad-term)
 - Symptomatic SARS-CoV-2 infection (CDC definition)
- To evaluate the impact of REGN10933+REGN10987 compared to placebo on the duration of signs and symptoms in seropositive subjects with symptomatic SARS-CoV-2 infection confirmed by RT-qPCR
- To evaluate the impact of REGN10933+REGN10987 compared to placebo in seropositive subjects on SARS-CoV-2 RT-qPCR viral load
- To evaluate the impact of REGN10933+REGN10987 compared to placebo in seropositive subjects on SARS-CoV-2 infection:
 - On health care utilization
 - On absenteeism from daily responsibilities (where applicable)

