Proportion of subjects with negative RT-qPCR (based on central lab test) regardless of serology status at baseline who subsequently have a positive SARS-CoV-2 RT-qPCR and symptomatic (CDC definition) SARS-CoV-2 infection during the EAP	B
Proportion of baseline-seronegative or baseline-seropositive subjects with negative RT-qPCR (based on central lab test) who subsequently have a positive SARS-CoV-2 RT-qPCR and symptomatic (CDC definition) SARS-CoV-2 infection during the EAP	B
Proportion of baseline-seropositive subjects (based on central lab test) who subsequently have a positive SARS-CoV-2 RT-qPCR during the EAP	B
Time-weighted average of viral load (log10 copies/mL) from the first positive SARS-CoV-2 RT-qPCR in NP swab sample (that has an onset during the EAP) until third weekly visit after the first positive test in seropositive subjects (based on central lab test) during the EAP	C
Time-weighted average of viral load (log10 copies/mL) from the first positive SARS-CoV-2 RT-qPCR in NP swab sample (that has an onset during the EAP) until the second weekly visit after the first positive test in seropositive subjects (based on central lab test) during the EAP	C
Area under the curve (AUC) in viral load (log10 copies/mL) in NP swab samples from the first positive SARS-CoV-2 RT-qPCR NP swab sample until the first confirmed negative test, in seropositive subjects (based on central lab test) that has an onset during the EAP	C
Note: Only for RT-qPCR positive subjects during the EAP with confirmed negative tests in the seronegative mFAS	
Proportion of subjects in placebo group who have a RT-qPCR confirmed SARS-CoV-2 infection (regardless of symptoms) during the EAP by the status of household members participating in study R10933-10987-COV-2067 and receiving REGN10933+REGN10987 or whose household member did not receive treatment with REGN10933+REGN10987	B
Proportion of subjects who have a RT-qPCR confirmed SARS-CoV-2 infection (regardless of symptoms) during the EAP by the status of household members participating in study R10933-10987-COV-2067 and receiving REGN10933+REGN10987	B
Proportion of subjects who have a RT-qPCR confirmed SARS-CoV-2 infection (regardless of symptoms) during the EAP by the status of household members receiving an approved monoclonal antibody treatment for COVID-19	B

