5.7.4. Analyses of Other Secondary and Exploratory Efficacy Variables

Other secondary efficacy endpoints will be analyzed by type of endpoint defined in Sections 4.5.2 to 4.5.8 for all cohorts. The analysis methods for key secondary efficacy endpoints in both cohort A and cohort B will also be applied to exploratory endpoints in both cohort A and cohort B if appropriate. Otherwise, the primary approach to the data will be descriptive statistics. For the comprehensive evaluation of efficacy, nominal p-values may be reported. Raw data descriptive statistics will also be presented.

Other secondary efficacy and exploratory endpoints for cohort A1 and cohort B1 may also be analyzed by type of endpoint. If the sample size is sufficient, continuous variables will be summarized by the descriptive statistics (e.g., n, mean, SD, Q1, median, Q3, minimum and maximum, etc.). Binary variables will be summarized using the number and percentage of subjects in each treatment group. No statistical hypothesis testing will be performed for cohort A1 and cohort B1. This approach may also be applied to adolescent subjects.

Binary Endpoints

Binary endpoints in cohort A and cohort B will be analyzed by applying the same approach used for the primary efficacy endpoints.

For endpoints regarding viral loads, visits with missing viral load (\log_{10} copies/mL) in NP swab samples will not be included in the analyses. For binary endpoints regarding the index case or household members linkage to R10933-10987-COV-2067 or subjects in cohort B, and endpoints regarding the medically attended visits, Fisher's exact test will be used. KM curves will be used to assess the exploratory endpoint of proportion of baseline-seronegative subjects who have a first RT-qPCR confirmed SARS-CoV-2 infection in the follow-up period.

Continuous Endpoints

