11. The investigator may perform a targeted physical exam, request an exam and/or vital signs at any time. These assessments can be performed using a clinic visit or a remote visit with the investigator or sub-investigator, or designee (ie, nurse practitioner in countries where allowed by local law).
12. For all women of childbearing potential (WOCBP) and girls at or beyond menarche, except subjects with a confirmed pregnancy. If the local urine pregnancy test is positive, the site must perform a serum pregnancy test for confirmation.
13. Samples for drug concentration and, immunogenicity, and laboratory testing will be collected based on the subject subset designation as indicated in [Table 7](#).
14. The serology test results will not be communicated to the sites. The sponsor's blinded study team will not have access to post-baseline results associated with subject identification until after the database is locked.
15. During each scheduled or unscheduled visit/contact, the investigator or designee will query subject about AEs in general (see Section 10.1.1 of the protocol) and evaluate if the AEs are associated with SARS-CoV-2 infection, including fever (see Section 9.2.2.2 of the protocol). The investigator should recommend that subjects (themselves or by their parent/guardian) measure their temperature daily during EAP, approximately at the same time, and also every time when the subject feels feverish, chills, or sick. Subjects with symptomatic SARS-CoV-2 infection should be queried on their symptoms weekly until symptoms resolve, even during follow-up period, then follow the regular schedule.
16. The information for the household assessment, including household members who receive an EUA approved monoclonal antibody treatment for COVID-19 or household members participating in the R10933-10987-COV-2067 study, should preferably be collected at the baseline visit. There will be a follow-up assessment at day 29.
17. All subjects will have a weekly NP swab sample collected during the EAP. Only subjects who are RT-qPCR positive will continue to have weekly NP swab samples collected during the follow-up period until 2 consecutive negative (≥ 24 hr) RT-qPCR results or the end of study visit.

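### The exploratory endpoints on household members' antibody treatment set no time limit on that treatment, so spread within the household can distort the comparison

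*SAP*

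**What the plan says.** **Exposure.** SAP 4.5.4 defines the exposure as infection status during the EAP "by the status of household members receiving an approved monoclonal antibody treatment for COVID-19". A companion endpoint pools that with REGN10933+REGN10987 received in COV-2067. Neither gives a date or a cut-off. Two neighbouring exploratory endpoints, based on COV-2067 participation alone, are undated too.

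**Objective.** It is causal and covers anyone in the home: "To evaluate the impact of treating any household member with anti-SARS-CoV-2 monoclonal antibody on the incidence of SARS-CoV-2 infection among their household contacts" (Protocol 2.1.4). SAP 1.2.3 repeats it: "To evaluate the impact of treating any household member with anti-SARS CoV-2 monoclonal antibody".

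**Data collection.** Protocol Table 3 footnote 16 covers household members' antibody treatment and adds "There will be a follow-up assessment at day 29". The SAP schedule (10.2.1, footnote 16) says the information "should preferably be collected at the baseline visit. There will be a follow-up assessment at day 29". Protocol 9.2.1, a section restricted by its heading to the screening/baseline visit, also lists "treatment with an EUA approved monoclonal antibody treatment for COVID-19" as part of the household assessment. The two places disagree on when the item is collected.

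**Later treatment of participants.** Protocol 8.10: "Subjects with symptomatic RT-qPCR confirmed SARS-CoV-2 infection during the study will be treated according to local standard of care".

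**Analysis.** SAP 5.7.4 sends binary endpoints to the primary-analysis approach (household GEE, with logistic regression as fallback). It reserves Fisher's exact test for a list that includes "For binary endpoints regarding the index case or household members linkage to R10933-10987-COV-2067 or subjects in cohort B". Nominal p-values may be reported.

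**The concern.** A causal question about treating one person and protecting another needs the treatment to come first. Exclusion criterion 2 (Protocol 7.2.2) bars subjects who live with a known infected person other than the index case(s). A treated non-index member was therefore mostly diagnosed after the subject's day 1, and may have caught the infection from the subject. Such members are found mainly in homes where the virus is spreading, and in those homes the subject's own risk is higher whatever the antibody does.

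If those households count as treated, the comparison no longer has a null of equal risk. The distortion runs toward harm: it can create an apparent adverse association or cancel a real protective one. Clustering by household corrects the standard error but leaves this bias, because the bias lies in the definition of exposure.

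**Working it through.** **1. The plan's own figures.** No figure is stated for these endpoints. The household structure comes from Protocol 11.2.1 and Table 9: 1248 subjects, 430 households, mean size 2.9, 10% placebo attack rate, correlation 0.1 to 0.6. A GEE simulation on that structure gives power 0.929, 0.943, 0.985 and 0.996 at correlations 0.1, 0.3, 0.5 and 0.6. The plan states 0.914, 0.956, 0.983 and 0.999, so all four agree within 2 points. Enrolment is 1248 / (0.9 × 0.7) = 1980.95, against 1980 stated. The structure is a fair base.

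**2. The mechanism by hand.** Take one subject, one other contact and an index case, with no antibody effect on anyone. Let p = infection risk, γ = within-household correlation, qI = chance the index case is treated, and qS = chance an infected contact is treated afterwards.

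- Subject's risk if the other contact is infected: p + γ(1 − p)
- Share exposed: e = qI + (1 − qI)·p·qS
- Exposed and infected: n = qI·p + (1 − qI)·p·qS·[p + γ(1 − p)]
- Risk if exposed: n/e. Risk if unexposed: (p − n)/(1 − e)

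With p = 0.10, qI = 0.10 and qS = 0.10, e = 0.10 + 0.90 × 0.01 = 0.109.

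- γ = 0: n = 0.010 + 0.009 × 0.10 = 0.0109. The risks are 0.100 and 0.100, OR 1.00.
- γ = 0.1: n = 0.010 + 0.009 × 0.19 = 0.01171. The risks are 0.1074 and 0.0991, OR 1.09.
- γ = 0.3: n = 0.010 + 0.009 × 0.37 = 0.01333. The risks are 0.1223 and 0.0973, OR 1.29.

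If qS = 0 (only index cases treated), n = qI·p and e = qI, so both risks equal p and there is no bias at any γ.

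**3. The full household structure.** Household size is taken as 1 + Poisson(1.9). A subject then has on average (1.9 + 2.9² − 2.9)/2.9 = 7.41/2.9 = 2.56 co-participants rather than one, so the distortion grows. The true effect is null, p = 0.10, and the test is a cluster-robust logistic test at 0.05 with 1000 runs per cell. qI and qS are assumptions. Each cell shows the median OR and the rejection rate when exposure has no cut-off.

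| qI | qS | γ = 0 | γ = 0.1 | γ = 0.3 | γ = 0.6 |
|---|---|---|---|---|---|
| 0.1 | 0.1 | 0.98, 4% | 1.19, 11% | 1.67, 37% | 2.53, 70% |
| 0.1 | 0.3 | 0.99, 6% | 1.45, 31% | 2.67, 93% | 5.55, 100% |
| 0.3 | 0.1 | 0.99, 4% | 1.09, 4% | 1.24, 16% | 1.53, 31% |
| 0.3 | 0.3 | 1.01, 7% | 1.24, 17% | 1.73, 64% | 2.77, 95% |

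With exposure limited to treatment before day 1, the median OR is 0.97 to 1.01 in every cell and the robust test rejects 4% to 8%. Fisher's test on that same baseline exposure still rejects about 5% to 22% once γ is 0.1 or more, because it ignores clustering. That is a separate fault and should not be credited to timing.

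**4. A lower treatment rate.** A qS of 0.3 is high. With qS from 0.02 to 0.20 and about 15% of index cases treated (also assumed), the median OR is 0.99 to 1.29 at γ = 0.1 and 1.05 to 1.92 at γ = 0.3, with rejection about 6% to 65%. With baseline exposure it is 0.94 to 1.02, with 4% to 7% rejection.

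**The case against.** **The documents never say that later treatment counts.** This is correct. A reader might infer from the day 29 update that it is counted by design. The text supports only that no cut-off exists, that baseline collection is preferred, and that Protocol 9.2.1 treats the item as baseline-only. That conflict does not supply a cut-off.

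**Few secondary cases would be treated.** Protocol 8.10 covers symptomatic subjects, 8.9 restricts treatment of asymptomatic infection, and 1.5 describes the antibody authorisations as limited to high-risk outpatients. In the administrative assessment 8 of 30 infected seronegative subjects were symptomatic (8 + 0 of 21 + 9; Protocol 3.2.5 and 3.2.6), about 27%. Treating 5% to 30% of those gives qS = 0.013 to 0.08. With infection at 10% and 5% by arm, the household-robust test then rejects 6% to 7% at correlation 0.1 and 8% to 16% at 0.3. The median OR across correlations 0.1 to 0.3 is 1.02 to 1.31. This stands for enrolled contacts. Household members who did not enrol may differ, and the documents give no rate for them.

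**Fisher's test is not planned for the approved-antibody endpoint.** Also correct: SAP 5.7.4 points that endpoint to the household GEE or logistic approach. Only the pooled endpoint could fall under the Fisher clause. Rejection rates from Fisher would overstate the timing problem.

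**The stakes are low.** This stands. The endpoints are exploratory, and the tables should not be read as a threat to the trial's conclusions.

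**Conclusion.** The gap is real but limited. The endpoints as defined allow treatment during follow-up to count as exposure, and positive within-household correlation then biases the comparison toward harm. The word is can, not will: the bias vanishes at zero correlation or if only index cases are treated, and it is small at correlation 0.1 with few treated contacts. A working range is OR 1.0 to 1.3 at correlation 0.1 and 1.05 to 1.9 at 0.3. It rests on assumed treatment of 2% to 20% of infected contacts and about 15% of index cases; more treated contacts or fewer treated index cases would raise it.

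A reader might extend the point to all the household-transmission evidence. The documents do not support that. The key secondary comparison by index-case treatment, and the other secondary comparison through COV-2067 or cohort B, contrast drug with placebo as randomised in those populations. No alpha-controlled result depends on the exploratory endpoints. Severity: minor.

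**What to change.** In SAP 4.5.4 and 5.7.4:

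- Define exposure for these endpoints as antibody given to a household member on or before the subject's day 1, taken from the baseline household assessment. Treatment first reported at day 29 does not count unless it is dated on or before day 1.
- If treatment dates are held, a time-dependent exposure that stops at the subject's first positive test is an acceptable alternative.
- Use the household-clustered primary-model approach (GEE or cluster-robust logistic) for the pooled endpoint as well, instead of Fisher's test.
- Report the result as a non-randomised estimate with a confidence interval.
- Reconcile Protocol 9.2.1 with Table 3 footnote 16 on when household treatment is recorded.

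**Cost.** Mostly wording. Subjects enter within 96 hours of the index case's test sample, so index cases treated shortly after day 1 become unexposed. Because of exclusion criterion 2, the baseline definition is in practice close to index-case-only and narrows the any-member objective. The time-dependent version keeps that objective but needs treatment dates, which footnote 16 and 9.2.1 do not say are collected.
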